## 5.0 Special Considerations

### 5.1 Health Insurance Portability and Accountability Act (HIPAA)

N/A

### 5.2 Family Educational Rights and Privacy Act (FERPA)

N/A

### 5.3 Code of Federal Regulations Title 45 Part 46 (Vulnerable Populations)

There will be no vulnerable populations involved.

#### A. Special Populations

### 5.4 General Data Protection Regulation (GDPR)

N/A

### 5.5 NJ Access to Medical Research Act (Surrogate Consent)

N/A

## 6.0 Data Management Plan

### 6.1 Data Analysis

Power analysis was completed to determine the sample size to be collected for each arm.

The results will be analyzed using t-tests and its nonparametric equivalent to determine if there is a difference in pain and anxiety scores between the two arms.

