### **1.3 Research Design and Methods**

#### **A. Research Procedures**

This will be a randomized control trial conducted in the gynecology clinic inside Robert Wood Johnson University Hospital (RWJ) and the offices of Rutgers Medical Group Obstetrics and Gynecology (RMG). A family planning attending alone at RMG or accompanied by obstetrics and gynecology (Ob/Gyn) residents at RWJ will perform all IUD insertions during this study period. Patients scheduled for an IUD, either the Mirena® (levonorgestrel-releasing intrauterine system 52 mg) or Paragard® (intrauterine copper contraceptive), at both locations will be instructed to take ibuprofen 30 minutes prior to their procedure.

Enrollment will occur during all weekdays at both RWJ and RMG. Eligible women will be able to read and write in English. Exclusion criteria include contraindications to IUD placement: Active pelvic infection, pregnancy, known distortion of uterine cavity, Wilson's disease (Paragard® only), breast cancer (Mirena® only). Eligible women will be enrolled if they are willing to be randomized. Written consent will be obtained from each participant.

After the consent process is completed, the patients will complete a survey which includes their demographic information, if they are currently menstruating, and their pregnancy history while sitting in the waiting room. The patient will also complete a 10 point visual analog scale (VAS) to report her baseline pain and a State Trait Anxiety Inventory (STAI). Vital signs will be recorded with an automated machine.

Participants will then be randomized to routine pain control measures or routine pain control measures plus music. Randomization will be completed by the study staff, who will open sequentially numbered, sealed, opaque envelopes. Allocation will be in a 1:1 ratio. Routine pain control will include instructions to take ibuprofen 600 mg 30 minutes prior to the procedure. These instructions will be given to all participants. It will be noted whether patients actually take ibuprofen or not by the study staff. Patients randomized to receive music in addition to routine pain control measures, will listen to preselected classical music played on the PI phone. Patients will control the volume.

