A study staff member will be present in the room throughout the duration of the procedure in addition to the physician performing the actual insertion of the IUD. This study staff member will complete a procedure information sheet including vitals, type of IUD inserted, and the VAS and STAI at several points of the procedure (immediately prior to the procedure, point of speculum insertion, point of tenaculum placement, point of IUD insertion, and 5 minutes post-procedure).

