**D. Endpoints**  
The primary endpoint is pain scores. The secondary endpoint is anxiety.

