#### **1.4 Preliminary Data**

There is no preliminary data.

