**1.9 Data Collection**

**A. Primary Data Collection**

- **Location:** At both RWJ and RMG, data collection will take place within two main areas: the waiting room and the patient exam room.
- **Process of Data Collection:** In the waiting room, patients will complete the demographic survey. They will also complete, the VAS and STAI for their baseline pain and anxiety scores, respectively. If the patient wishes to complete any of these instruments in private, she will be led into an unoccupied patient exam room. In the exam room, the providers will complete the provider survey regarding the patient. The providers will also record vital signs, BMI, and other pertinent medical information. While in the exam room, at several points through the insertion the VAS and STAI will be administered.
- **Timing and Frequency:** The patient survey will be completed once by the patient while she is in the waiting room. The provider survey will be completed once by the provider while the patient is in the exam room. The VAS will be completed by the patient at several points: immediately prior to the procedure, point of speculum insertion, point of tenaculum placement, point of IUD insertion, and 5 minutes post-procedure. The STAI will be completed immediately prior to the procedure and 5 minutes post-procedure.
- **Procedures for Audio/Visual Recording:** There will be no audio or video recordings of the patients.

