- **Study Instruments:** The patient survey will include demographic information including: age, ethnicity, preferred language, marital status, education level, history of smoking, history of alcohol use, current medications, allergies, date of last menstrual period, menstrual history, exercise habits, current pain level, current anxiety level, history of depression, music interests, prior medical procedures, prior medical complications, pregnancy history, delivery history, miscarriage history, previous pain management techniques, and preferred method of music listening. The provider survey includes heart rate, blood pressure, respiration rate, body mass index (BMI), type of IUD inserted, medical complications, prior contraceptive use, gravidity, parity. The VAS is a well known and accepted instrument for quantifying pain. It has been used previously to report pain during IUD insertion (Mody 2018). The STAI is also a well known and accepted instrument for quantifying anxiety. It, too, has also been used previously to report anxiety in several different circumstances (Kendall 1976).
- **Ethnographic Studies, Interviews, Or Observation:** N/A
- **Subject Identifiers:** N/A

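### Section 6.1 leaves the pre-randomization pain and anxiety scores unused; a prespecified ANCOVA would be a cheap gain in precision, though the planned t-test is valid

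*Combined protocol and SAP*

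**What the plan says.** Section 6.1 (Data Analysis) contains the only statement of method: "The results will be analyzed using t-tests and its nonparametric equivalent to determine if there is a difference in pain and anxiety scores" between the arms. No covariate, regression model or change-from-baseline analysis is named there or elsewhere.

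The material for an adjusted analysis is already in the data collection plan:

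- **Baseline scores.** Section 1.9 A has patients in the waiting room fill in a demographic survey, and then: "They will also complete, the VAS and STAI for their baseline pain and anxiety scores, respectively". Section 1.3 A describes the same step.
- **Order.** Section 1.3 A places allocation after those scores: "Participants will then be randomized to routine pain control measures or routine pain control measures plus music". Allocation is 1:1 by sealed envelope, and no stratification is described.
- **Parity.** The provider survey in section 1.9 A includes "type of IUD inserted, medical complications, prior contraceptive use, gravidity, parity". Pregnancy history is also taken on the waiting-room survey.
- **Later scores.** The in-room procedure sheet in section 1.3 A records scores at these points: "immediately prior to the procedure, point of speculum insertion, point of tenaculum placement, point of IUD insertion, and 5 minutes post-procedure". All of them come after allocation.

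Section 1.3 D defines the endpoints without a time point: "The primary endpoint is pain scores. The secondary endpoint is anxiety".

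**The concern.** A score measured before randomization that predicts the outcome can be used to remove part of the between-woman variation from the treatment comparison. The same 96 women then give a narrower confidence interval. This plan collects such scores and does not use them.

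There is also nothing in the design to absorb chance imbalance. With 48 per arm, the difference between arms in a baseline mean has a standard deviation of √(2/48) = 0.204 baseline SDs. A difference of up to 1.96 × 0.204 = 0.40 SD would therefore be unremarkable. The t-test stays valid on average over such imbalances, but it does not adjust for the one that occurs.

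Timing matters for two reasons. The surveys hold more than twenty items, so covariates picked after the data are seen would invite the charge of selection. And the score taken in the exam room just before the procedure could be mistaken for a baseline. It follows allocation, so adjusting for it could remove part of any effect of music.

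**Working it through.** **Inputs.** From section 1.5: difference 2 points, SD 3, two-sided alpha 0.05, power at least 90%, 48 per arm. From section 1.3 A: 1:1 allocation. R², the share of outcome variance explained by baseline VAS and parity, is an assumption shown as a range, because section 1.4 states: "There is no preliminary data".

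**Step 1: reproduce the plan's figure.**
n per arm = 2 × [(1.960 + 1.282) × 3 / 2]² = 47.28, rounded up to 48. The stated 48 reproduces. That formula is the normal approximation, under which power at 48 is 90.4%. By the noncentral t distribution it is 89.8%, and 49 per arm would be needed for 90%.

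**Step 2: unadjusted t-test, 94 degrees of freedom.**
Standard error = 3 × √(2/48) = 0.612. Half-width of the 95% CI = 1.9855 × 0.6124 = 1.216. Noncentrality = 2 / 0.612 = 3.266. Power = 89.8%.

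**Step 3: ANCOVA with k = 2 covariates, 92 degrees of freedom.**
Adjustment multiplies the residual variance by (1 − R²). Fitting the covariates inflates the variance of the treatment estimate by an expected factor of 1 + k/(N − k − 3) = 1 + 2/91 = 1.022, with N = 96. So:

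Standard error = 3 × √[(1 − R²) × 1.022 × 2/48]

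Example at R² = 10%: standard error = 3 × √(0.90 × 1.022 × 2/48) = 0.587. Half-width = 1.986 × 0.587 = 1.166. Noncentrality = 2 / 0.587 = 3.405. Power = 92.1%.

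Effective N = 96 / [(1 − R²) × 1.022].

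| Assumed R² | Power, variance reduction only | Power, full cost | Half-width, full cost | Effective N |
|---|---|---|---|---|
| 0% | 89.8% | 89.2% | 1.230 | 93.9 |
| 1% | 90.1% | 89.5% | 1.223 | 94.9 |
| 5% | 91.2% | 90.7% | 1.198 | 98.9 |
| 10% | 92.6% | 92.1% | 1.166 | 104.4 |
| 25% | 96.2% | 95.8% | 1.065 | 125.2 |

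The full-cost columns are the ones to read. At 5%, 10% and 25% the adjustment is worth about 3, 8 and 29 extra women. A simulation of 40,000 trials per row, with one continuous and one 50%-prevalence covariate, gave ANCOVA power of 89.2%, 89.6%, 90.7%, 92.1% and 95.8% for the five rows.

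**Step 4: break-even.** The adjusted half-width equals 1.216 when (1 − R²) × 1.022 × (1.9861/1.9855)² = 1, that is at R² of about 2.2%. With one covariate the inflation is 1 + 1/92 = 1.011, break-even is about 1.1%, and power at R² = 0 is 89.5%.

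No such calculation can be made for STAI, because the documents give neither an SD nor a target difference for it.

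**The case against.** The strongest reply is that nothing here is broken. The unadjusted comparison is unbiased under 1:1 randomization and is the analysis for which the trial was sized. The benefit rests on an R² that the documents do not supply. Waiting-room pain may be close to zero for most women and may say little about pain at insertion. At R² = 1% ANCOVA is slightly worse (89.5% against 89.8%), at 5% it is worth about three women, and nothing in the documents supports 25%. For anxiety the gain cannot be quantified at all.

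All of that is true, and it sets the level of the point: a recommended improvement, not a correction. It does not remove the point, because the possible loss is small and bounded while the possible gain is several times larger.

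Two narrower objections also have some force:

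- The Timing and Frequency item in section 1.9 A starts both instruments just before the procedure and omits the waiting-room administration. This does not cancel the explicit waiting-room scores in sections 1.3 A and 1.9 A, but the text should be made consistent, since the adjustment depends on the two being separate measurements.
- Parity sits on a form completed in the exam room. Music cannot alter it, so it remains an acceptable covariate, and the waiting-room pregnancy history offers an earlier source.

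**Conclusion.** The point holds as a low-cost improvement. Section 6.1 plans only unadjusted tests although suitable pre-randomization covariates are collected. At 48 per arm, SD 3 and a 2-point difference, adjustment for two covariates changes power by −0.6 point at R² = 0 (89.8% to 89.2%), +0.9 at 5%, +2.3 at 10% and +6.0 at 25%. The half-width moves from 1.216 to 1.230, 1.198, 1.166 and 1.065 respectively.

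These figures assume the SD in section 1.5, complete data on 96 women and a linear model for a bounded 10-point scale. Which row applies cannot be known from the documents. Below an R² of about 2.2% there is a slight net loss.

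**What to change.** In section 6.1:

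1. Make the primary pain analysis a linear model (ANCOVA) of VAS at one named time point on arm, adjusted for waiting-room VAS and parity (nulliparous or parous). The time point has to be chosen first; VAS at IUD insertion is one candidate.
2. Analyze STAI at 5 minutes after the procedure in the same way, with waiting-room STAI as the baseline covariate.
3. Define baseline as the waiting-room score taken before allocation, and state that the in-room pre-procedure score is not a covariate. Bring the Timing and Frequency item in section 1.9 A into line.
4. Report adjusted mean differences with 95% confidence intervals, and keep the t-test and the rank test as sensitivity analyses.

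Site and planned IUD type are optional additions. Neither is a listed survey item now (only the type actually inserted is), so each would need a line on a form completed before allocation.

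The cost is a few sentences, a few lines of code and about 0.6 percentage point of power if the covariates explain nothing. The core model needs no new data. The change must be made before outcome data are examined.

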## **6.2 Data Security**

All forms completed during the patient encounter (consent form, patient survey, provider survey, VAS, STAI) will immediately be locked in [name] office. Once this data is transcribed into electronic form, the paper forms will be discarded in HIPAA compliant bins. The electronic data will be stored on an encrypted hospital computer. No identifying data will be collected.

## **6.3 Data and Safety Monitoring**

This research poses only minimal risk to the patient.

### **A. Data/Safety Monitoring Plan**

N/A

### **B. Data/Safety Monitoring Board Details**

N/A

## **6.4 Reporting Results**

### **A. Individual Subjects' Results**

The results of the study will not be shared with the subjects.

### **B. Aggregate Results**

Aggregate study results will not be shared with subjects.

### **C. Professional Reporting**

The results of this research are intended to be published in order to be shared with the scientific community.

### **D. Clinical Trials Registration, Results Reporting and Consent Posting**

N/A

## **6.5 Secondary Use of the Data**

There are no plans for secondary use of the data.

## **7.0 Research Repositories – Specimens and/or Data**

The data collected in the course of this research will not be stored for future research. No specimens will be collected.

## **8.0 Approvals/Authorizations**

A letter of cooperation from Robert Wood Johnson University Hospital will be obtained prior to commencing research at RWJ.

